5.3 Subject Exclusion Criteria

An individual who meets any of the following criteria will be excluded from participation in this study:

- Patient is pregnant.
- Patient has pacemaker or implantable defibrillators (These have not been bench tested as of September 2016).
- Patient has known or suspected nickel allergy.
- Patient is scheduled or receiving *investigational* drugs for neoadjuvant regimen. (This could confound UADE of this device.)
- Patient has any condition that would place the individual at increased risk or preclude the individual's full compliance with or completion of the study.
- Patient has other malignancy except for adequately treated and cured basal or squamous cancer, curatively treated in situ disease or any other cancer for which the patient has been disease free for greater than or equal to 5 years.

5.4 Strategies for Recruitment and Retention

Screening/Enrollment: the investigator will identify subjects from his/her current patient referrals, MHS Breast Tumor Board, and Routine Clinical Preview of Scheduled MHS Breast Patients who may meet inclusion/exclusion criteria. The investigator will determine the interest of the subject to take part in the study. If the subject agrees, the investigator or research nurse will approach the patient to obtain informed consent. Inclusion/exclusion criteria will be verified by the research nurse prior to scheduling the subject for the SAVI SCOUT procedure.

5.5 Treatment Assignment Procedures

In this pilot study, all patients will receive the same treatment assignment, i.e. lesion(s) localization with the SCOUT device(s) 31 - 365 days prior to surgery. Neoadjuvant treatment decisions will be determined by patient's medical oncologist.

5.6 Subject Withdrawal

5.6.1 Withdrawal Procedures

Subjects are free to withdraw from participation in the study at any time upon request. An investigator may terminate a study subject's participation in the study if:

- Any clinical adverse event (AE), laboratory abnormality, or other medical condition or situation occurs such that continued participation in the study would not be in the best interest of the subject.
- The subject meets an exclusion criterion (either newly developed or not previously recognized) that precludes further study participation.
- The subject may elect to withdraw for any reason. However, the subject must either allow for needle-guided (non-surgical) removal by the radiologist or sign a release of records that allows the PI to validate surgical excision at an outside facility.

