5.2 Subject Inclusion Criteria

In order to be eligible to participate in this study, an individual must meet all of the following criteria:

- Patient is willing and able to provide informed consent. Patient SCOUT device(s) is placed as part of routine care or study at any time but before neoadjuvant treatment begins.
- Patient is female.
- Patient is between the ages of 18 and 90 years.
- Patient has breast cancer and will undergo neoadjuvant therapy and excision at Memorial Healthcare System.
- Patient is willing and able to comply with all study procedures and be available to follow-up for the duration of the study (1 - 13 months).
- Patient reads or understands English or Spanish.

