7.2 Enrollment/Baseline (Study Visit 1 - 31-365 days prior to surgery)

- Patient has SAVI SCOUT LOCALIZATION by Radiologist at any time prior to neoadjuvant treatment SAVI SCOUT placed anytime FDA clearance 10/31/17
- Verify inclusion/exclusion criteria.
- Surgeon and/or MCI research nurse/Investigator
 - complete the **Patient Inclusion/Exclusion Eligibility Enrollment Form**.
 - obtain **consent** from subject on **Informed Consent Form**: Before or after SAVI SCOUT LOCALIZATION and PRIOR TO NACT
 - complete **the Documentation of Consenting Process Form**
- **Research Radiologist**
 - Verifies inclusion/exclusion criteria and Assigns Study ID
 - Completes Device(s) Placement Form
 - *Sends Copy of Consent and Study ID sent to OHR for tracking.*

Sometimes, additional studies ordered by Med-Onc can impact surgical plan.

7.3 Device Placement and Post-Implant Verification (Study Visit 2, Day 0-30 days prior to surgery)

**Breast Radiologist completed standard of care pre-operative skin marking*

Research Radiologist

Completes the Device Placement Form [Device Placement Recheck]] on standard of care imaging and performs audio verification and repeat skin marking if requested as standard of care by surgeon.

If not verified, the surgeon must be notified to determine whether the patient must be scheduled for a second localization procedure 0 - 365 days prior to surgery.

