11.3 Informed Consent Process

Informed consent is a process that is initiated prior to the individual agreeing to participate in the study and continues throughout study participation. Extensive discussion of risks and possible benefits of study participation will be provided to subjects and their families, if applicable. A consent form describing in detail the study procedures and risks will be given to the subject. Consent forms will be IRB-approved, and the subject is required to read and review the document or have the document read to him or her. The investigator or designee will explain the research study to the subject and answer any questions that may arise. Patients may have SAVI SCOUT LOCALIZATION by the Radiologist at any time prior to NACT as SAVI SCOUTs may be placed anytime per FDA clearance 10/31/17 (2). The subject will sign the informed consent document prior to any study-related activities. Subjects

will be given the opportunity to discuss the study with their surrogates or think about it prior to agreeing to participate. They may withdraw consent at any time throughout the course of the study. A copy of the signed informed consent document will be given to subjects for their records. The rights and welfare of the subjects will be protected by emphasizing that the quality of their clinical care will not be adversely affected if they decline to participate or withdraw from this study. The consent process will be documented in the clinical or research record.

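### Section 5.6.1 attaches an obligation to an unconditional right to withdraw, and its two options leave out the subject who keeps her planned excision at Memorial Healthcare System (MHS)

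*Combined protocol and SAP*

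**What the plan says.** Section 5.6.1 opens with an unqualified right: "Subjects are free to withdraw from participation in the study at any time upon request". Its last bullet repeats that withdrawal may be for any reason, and then adds a requirement: "the subject must either allow for needle-guided (non-surgical) removal by the radiologist or sign a release of records". The purpose given for the release is to let the principal investigator "validate surgical excision at an outside facility".

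Section 11.3 states the right again, with no condition: "They may withdraw consent at any time throughout the course of the study". It also commits the study to stressing to subjects that the quality of their "clinical care will not be adversely affected if they decline to participate or withdraw from this study".

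Two other parts of the protocol show whom the rule covers. Under section 5.2 each subject "will undergo neoadjuvant therapy and excision at Memorial Healthcare System", and the same section says of the device: "Patient SCOUT device(s) is placed as part of routine care or study at any time but before neoadjuvant treatment begins". Section 7.2 allows consent to be taken "Before or after SAVI SCOUT LOCALIZATION and PRIOR TO NACT", so the device may already be in place when a subject joins the research.

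**The concern.** Two things are wrong with the last bullet of 5.6.1.

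- **Conflict.** An unconditional right is followed by an obligation. A withdrawing subject owes either a procedure or a signed release. The protocol does not say what happens if she agrees to neither, so staff have no instruction for that case.
- **Omission.** The two options suit a subject who leaves MHS with the device in place. They do not suit one who stops taking part in the research but keeps her standard-of-care operation at MHS. Her clinical need for the localizer does not end with her participation. Read literally, she must have it taken out by needle or sign a release for surgery elsewhere that she is not having.

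At stake is an unneeded needle procedure and the loss of a device placed for her care, against the assurance in section 11.3. For a subject who has surgery elsewhere the stake is smaller: the release is non-invasive, and the only fault is that it is required instead of requested.

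**Working it through.** The plan gives no figure on this point and no formula applies, so the check is a comparison of texts.

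**1. Right against duty.** The opening line of 5.6.1 and section 11.3 both give the right without qualification. The last bullet of 5.6.1 is mandatory in form. No section reconciles them, and none says that withdrawal is refused or penalised when both options are declined.

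**2. Options against the possible situations of a withdrawing subject with a device in place.**

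| Situation | Needle removal | Release for outside excision |
|---|---|---|
| Surgery at another facility | Possible | Fits |
| No surgery planned, or she wants the device out | Fits | Does not apply |
| Planned excision kept at MHS | Takes away the localizer she needs | Does not apply |

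The third row is the situation in which section 5.2 expects every subject to be at entry.

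**3. Whether the device belongs to the research or to her care.** Section 5.2 allows placement as routine care and section 7.2 allows consent after placement. Section 2.3.4 expects the great majority of these patients to receive the device before surgery in any case. Excision is labelled standard of care in section 7.4. For many subjects, therefore, the localizer is part of treatment that continues after withdrawal.

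**4. What losing it could mean.** Section 2.2 gives as the reason for early placement that, after a treatment response, image-guided localization is often harder and less reliable. A subject whose device is removed after such a response could face that problem. One who withdraws before or early in treatment would be less exposed to it.

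**5. Whether the duty is needed to confirm retrieval at MHS.** Section 6.2.2 already has a standard-of-care specimen radiograph read to verify that the device and lesion are in the specimen. For surgery at MHS, neither option in 5.6.1 adds to that check.

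**6. Whether needle removal is described anywhere else.** It does not appear in the risks (2.3.1), the procedures (6.2) or the schedule (section 7). The bullet thus names as one of two required options a procedure whose technique and risks the protocol does not set out.

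**7. Whom the wording covers.** Enrolment is 25 to 35 subjects. The period at risk is the part of the 31 to 365 days between placement and surgery (section 5.5) that follows consent. Section 5.1 estimates that 20% of subjects may need more than one device, up to four:

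- 0.20 × 25 = 5 subjects
- 0.20 × 35 = 7 subjects

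For a withdrawing subject in that group, literal compliance could mean more than one needle removal. These are counts among all enrolled subjects, not among those who withdraw. They describe the reach of the wording and do not count harm. The protocol gives no withdrawal rate and none is assumed here.

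**The case against.** The strongest reply is that the sentence is a safety step for accounting for a temporary implant (section 6.1) and not a bar to leaving. Withdrawal is granted twice in 5.6.1 and again in 11.3, no consequence is attached to refusal, and one of the two options involves no procedure. Because the release mentions an outside facility, the sentence most naturally addresses a subject who is leaving MHS. For one who stays, sensible staff would simply let the planned operation go ahead. If a localizer were lost, sections 2.3.3 and 6.2.1 describe placing a second device or a wire at no cost to the patient. The consent form may also deal with the matter.

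Much of this is fair. Confirming retrieval is the likely aim, exposure is hypothetical, and no effect on the endpoint is in question. What does not follow is that the text can stand:

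- A duty with no stated consequence is still a duty.
- Relying on staff to disregard it sits badly with section 12.3, which commits investigators to keep closely to the protocol.
- The second-localizer route is written for devices that cannot be detected or have moved, not for devices removed because of withdrawal.
- The consent form is not in the reviewed text, so its wording cannot be checked. Nothing is held against the plan on that account, but a better consent form would not correct 5.6.1.

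One caution carries over to the remedy. Making confirmation voluntary weakens the only retrieval check stated for a subject who leaves MHS with a device in place, and that is a safety matter as well as a record-keeping one.

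**Conclusion.** The concern holds on the text. Section 5.6.1 attaches a mandatory choice to a right that it and section 11.3 state without conditions, and the choice leaves out the subject whose excision stays at MHS. This should be corrected for patient protection; no bias, loss of precision or change in sample size is claimed. The number of subjects affected is unknown and may be zero.

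Confidence is high about what the wording says and omits. That anyone would be harmed is less certain, since it depends on staff applying the sentence literally to a subject who withdraws with a device in place and keeps her MHS surgery.

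**What to change.** Replace the second sentence of the voluntary-withdrawal bullet in 5.6.1, the one that imposes the two options, with text such as:

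> Withdrawal is not conditional on any procedure or release. If a device is in place, the subject may proceed to planned excision at MHS, have it excised elsewhere, or have needle-guided removal if she wants it or it is clinically indicated. She will be asked, but not required, to permit the PI to confirm device retrieval from the MHS or outside record.

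It would be tidy in the same edit to move the voluntary-withdrawal bullet out of the list of grounds on which an investigator may end participation, where it does not belong.

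The cost is a short protocol amendment with the IRB review that section 11.2 requires. The consent form needs changing only if it repeats the condition. The drawback is that retrieval may remain unconfirmed in the study file for a subject who declines. This matters most for one operated on elsewhere, so the request should be made and documented with care.

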5.7 Premature Termination or Suspension of Study

Unanticipated Adverse Device Effects (UADE): The sponsor must immediately conduct an evaluation of any unanticipated adverse device effect. A sponsor who determines that an unanticipated adverse device effect presents an unreasonable risk to subjects must terminate all investigations or parts of the investigations presenting that risk as soon as possible. Termination must occur no later than 5 working days after the sponsor makes this determination and no later than 15 working days after the sponsor was first notified of any UADE or other medical condition in which continued participation in the study would not be in the best interest of the subject.

This study may be suspended or prematurely terminated if there is sufficient reasonable cause. Written notification, documenting the reason for study suspension or termination, will be provided by the suspending or terminating party to the PI and Study Coordinator. If the study is prematurely terminated or suspended, the principal investigator will promptly

inform the IRB and will provide the reason(s) for termination or suspension. Circumstances that may warrant termination include, but are not limited to:

- Determination of unexpected, significant, or unacceptable risk to subjects.
- Insufficient adherence to protocol requirements.
- Data are not sufficiently complete and/or evaluable.
- Determination of futility.

In compliance with 21 CFR 812.46, if an unanticipated adverse device effect is determined by the sponsor as an unreasonable risk to subjects, termination of the study will occur no later than five (5) working days after the sponsor first receive notice of the effect. The study will not resume without IRB approval and FDA approval.

6. INVESTIGATIONAL INTERVENTION:

6.1 Study Product Description

Commercially available FDA cleared SAVI SCOUT Breast Localization and Surgical Guidance System (Cianna Medical, Inc.), including the console, PROBES and the temporarily implantable devices will be purchased for this study.

6.1.1 Acquisition

Additional replacement SCOUT devices will be supplied by the device manufacturer, Cianna Medical, Inc., to study subjects at no additional charge if a second device placement is required in the 0 - 365 day pre-operative time period.

6.1.2 Product Storage and Stability

The SCOUT devices will be stored per manufacturer specifications. Devices will be labelled consistent with CFR 812.5 "Caution – Investigational Device. Limited by Federal (or United States) law to investigational use." Device Accountability that there will be none as SCOUT devices has regulatory authorization to market the device or state whether or not you are going to track the device accountability. SCOUT devices that have been excised and would otherwise be discarded by pathology department after 3 - 4 weeks may be shared with the device manufacturer for purposes of scientific review. This will occur after standard of care pathology department protocol time period has elapsed.

6.2 Study Procedural Intervention(s) Description

6.2.1 Placement of SCOUT Device

Investigator will read over the informed consent (English or Spanish) with potential participants and ensure that they understand the study.

All participants will be given a copy of the informed consent document for their own

reference. Possible participants will be given as much time as is necessary to make an informed decision about whether to take part in the study. The informed consent document reminds them to take their time to make their decision and to discuss the decision with their friends, family and health care team. The study physician will allow the patient to ask as many questions as they want about the process before making an informed decision as whether to take part in the study. Family members will also be encouraged to ask questions and remain involved in the subject's medical care.

Neoadjuvant treatment will be determined by experienced medical oncologist. The breast radiologists are experienced with the device placement and verification techniques (standard of care). The study device(s) will be inserted 31 - 365 days prior to surgery with standard of care technique: image-guidance, local anesthetic, and 16-g needle used to percutaneously deploy the SCOUT device at the target lesion(s). Standard of care post-procedure image verification, audio verification, and skin marking will be performed. SCOUT position will be measured relative to the center of the target lesion(s) will be consistently measured on all breast imaging mammogram/ ultrasound images until surgical excision is confirmed. These measurement will determine whether or not migration > 5 mm occurs in days 0 - 365 days prior to surgery.

Up to 30 days prior to surgery, the standard of care device image verification and skin marking will be performed (at no charge to patient). This visit is performed as standard of care visit, usually within 7 days pre-operatively, and is coordinated with patient's other routine appointments in the same building, such as pre-admission testing. If the SCOUT device(s) is not verified in accurate and stable position (within 5 mm of initial placement as measured on mammogram and/or ultrasound imaging), the surgeon will be notified to determine whether a second localization device or wire placement will be needed. If requested, the placement of a second device using Radiology standard of care technique will be arranged at no expense to the patient up to 30 days prior to surgery.

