2.2 Rationale

The SAVI SCOUT (Cianna Medical, Inc.) surgical guidance system received 510(k) U.S. Food and Drug Administration (FDA) approval in August 2014 (1). FDA clearance for long-term use was approved in October 2017 (2). This system is currently used as standard of care since 2015 in the MHS operating rooms by experienced breast surgeons (over 600 MHS breast cancer patients and over 28,000 U.S. breast cancer patients as of September 2016) (3, 5). MHS standard of care practice, the device(s) is placed at the target lesion(s) under image-guidance by the radiologist up to 365 days prior to surgery.

Patients with certain types of breast cancer undergo neoadjuvant treatment with biologic (hormonal) and/or chemotherapy with the goal of decreasing the tumor volume prior to definitive surgery. If the original cancer lesion(s) resolve completely, this is called complete pathologic response (pCR) (4). pCR and even a partial response, while good for the patient, can result in disappearance or poor visualization of the target and often render pre-operative image-guided localization by the radiologist more difficult and less reliable. This can result in unintended larger, more disfiguring breast cancer surgery. Therefore, if the SCOUT device(s) can be placed prior to treatment response, when the lesion(s) is clearly visualized on imaging, accurate image-guided targeting is optimal and thus placement and subsequent surgery should be more accurate. If this pilot study demonstrates successful performance of the device without device-related complications, it will bring improved value to future patients who will require fewer and/or less extensive pre-operative and surgical procedures. Some value may also be provided to subjects as the targeting before tumor shrinkage is expected to be more accurate.

During the excisional procedure, the surgeon uses the console and PROBE to locate the SCOUT device(s) and breast and/or axillary tissue for targeted excision.

This pilot study will assess the performance of FDA cleared SCOUT system over a longer duration prior to breast and/or axillary lymph node surgery.

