2.3 Potential Risks and Benefits

2.3.1 Potential Risks

The risks of SCOUT localization are similar to or less than wire localization: bleeding, injury to vessels, adjacent tissue injury, pain, infection and repeating the procedure.

The most significant risk for this study is if the surgeon may not be able to successfully excise the device and/or target lesion. This has not occurred to date in our clinical (>150 patients) experience at MHS with our experienced breast surgeons.

Another potential risk to the patients is that the SCOUT device(s) might move during the 31-365 day time period. This could possibly require a longer procedure to remove the lesion(s) and/or retrieve the device(s). This has occurred to date in our clinical experience in less than

1% of our initial 150 patients, which is less than the device risk of wire migration (2 - 3%) which has been reported in the US for over 30 years.

Furthermore, standard wire localization procedures may require a second surgery to re-excise and get clear margins. Standard wire localization re-excision rate is reported by the American Society of Breast Surgeons as 20 - 40% nationally. However, the rate of positive margins with SCOUT localization is non-inferior or better than wire localization (1).

2.3.2 *Potential Benefits*

If long-term SCOUT device(s) localization is successful, neo-adjuvant therapy patients should be able to avoid some of the common and costly limitations associated with standard localization. After neo-adjuvant therapy, lesions are incompletely visualized for targeting. This can lead to: multiple additional pre-operative procedures, more complex and costly MR-guided procedures, and additional surgical procedures to fully excise the target lesion(s). We believe that use of the SCOUT localization procedure might lead to improved excision of the targeted tumor bed, fewer breast procedures, a reduced need for additional operations for margin re-excision and more convenience for the patient, operating room, surgeon, and radiologist scheduling. This will result in lower costs. In addition, the non-wire SCOUT offers surgeons more surgical access options for improved oncologic and cosmetic results (1).

2.3.3 *Minimization of Risks*

IRB approval is required prior to screening and enrollment. Subjects are required to provide signed informed consent prior to participation.

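### As worded, the 5 mm migration endpoint is measured from the centre of a lesion that treatment aims to shrink, so a motionless device can be counted as migrated or have no value

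*Combined protocol and SAP*

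**What the plan says.** The stability endpoint (Protocol Summary and section 4.1.2) limits SCOUT migration to 5 mm before surgery, measured on routine mammogram and/or ultrasound. It names no reference point.

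Section 6.2.1 supplies one. It states that "SCOUT position will be measured relative to the center of the target lesion(s", that position "will be consistently measured on all breast imaging mammogram/ ultrasound images until surgical excision is confirmed", and then: "These measurement will determine whether or not migration > 5 mm occurs in days 0 - 365 days prior to surgery".

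Later in the same section, the pre-operative check applies the same limit in other words: "within 5 mm of initial placement as measured on mammogram and/or ultrasound imaging". It does not say how the initial position is to be found again on a later image.

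On the lesion itself, section 2.2 describes neoadjuvant treatment as given "with the goal of decreasing the tumor volume prior to definitive surgery" and says that response "can result in disappearance or poor visualization of the target". Section 2.3.2 adds: "After neo-adjuvant therapy, lesions are incompletely visualized for targeting". Section 5.2 requires the device to be placed before that treatment starts, so any change in the lesion comes after the baseline measurement.

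Section 9.2 plans simple statistics only. No section that we could read says how a device is counted when its position cannot be measured.

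**The concern.** A migration measure needs a landmark that stays put. Here the landmark is the centre of the tissue that treatment is meant to remove, and the protocol's own rationale says it may be hard or impossible to see by the time of surgery.

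Two things can follow if the text is applied as written. When the lesion regresses unevenly, its centre moves, and a device that has not moved can appear to have migrated. When the lesion disappears, there is nothing to measure from. Those missing values would tend to fall in the patients who responded best, and section 2.2 gives that situation as the reason for placing the device early. The stability rate could then mix tumour response with device movement and be selectively incomplete.

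**Working it through.** The plan gives no calculation for this endpoint, so there is no figure to reproduce. The check is geometric.

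**Inputs from the documents.** Limit 5 mm (section 4.1.2); reference at the lesion centre (section 6.2.1); 25 to 35 patients (section 9.1).

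**Assumptions.** The documents give no lesion size, pattern of regression or centre shift. I therefore let the centre shift by s mm and keep the device fixed at position x relative to the original centre. Device positions are taken as uniform within a radius R of 3, 5 or 10 mm, in two or three dimensions. The 10 mm value matches the 1 cm placement criterion in section 4.1.2.

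**Step 1: when can a motionless device be misread?** After the shift, its relative position is x − s. If only distance is recorded, the change is | |x − s| − |x| |, which by the triangle inequality is at most s. So for s ≤ 5 mm the result is 0%. If position with direction is recorded, the change equals s exactly: 0% at s ≤ 5 mm and, by definition, 100% above it.

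**Step 2: what shrinkage does that require?** If one edge of the lesion stays fixed while the diameter falls from D to d, then s = (D − d)/2. For s > 5 mm the diameter must fall by more than 10 mm. For example, 20 to 5 mm gives s = 7.5 mm, and 30 to 10 mm gives s = 10 mm. Concentric shrinkage without tissue contraction gives s = 0, hence 0%.

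**Step 3: how often, if only distance is recorded?** Simulated share of motionless devices whose distance to the centre changes by more than 5 mm (2,000,000 positions per case), range over R = 3 to 10 mm and two or three dimensions:

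| Centre shift s | Misread as migrated |
|---|---|
| 5 mm | 0% |
| 5.5 mm | 9-29% |
| 7.5 mm | 35-68% |
| 10 mm | 55-97% |

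At 7.5 mm the individual results (two/three dimensions) are 67.6%/65.7% for R = 3, 53.3%/47.3% for R = 5 and 48.6%/35.2% for R = 10.

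**Step 4: missing values.** With m unmeasurable patients among n (one device each), the stability rate lies between (stable)/n and (stable + m)/n, a width of m/n. Each such patient adds 1/35 = 2.9 to 1/25 = 4.0 percentage points.

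**Step 5: the same device under a fixed reference.** Measured from its own position at placement, a motionless device has a displacement of 0 mm whatever the lesion does, apart from measurement error. It also keeps a value when the lesion has gone.

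**The case against.** **The sentence is damaged.** Its two verb phrases are run together, and it may have been meant to join a day-0 accuracy measure with a separate follow-up measure. The Device Placement Form, on which the recheck is recorded, is held outside the protocol and was not seen; it may settle the reference. This stands as a limit on what can be said about intent or practice. It does not remove the point, because no text that we could read replaces the lesion centre as the reference for the endpoint.

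**The two statements in section 6.2.1 may be one rule.** A reader might infer that the section contradicts itself. That is possible but not established. One statement names a reference point and the other a baseline, so they can be read together as lesion-centre position compared with its value at initial placement. That reading keeps the weakness, since the centre can still move or vanish. The two statements need reconciling either way.

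**The percentages could be mistaken for an error rate.** They are not one. The 35-68% figure belongs to one assumed shift, and the full range runs from 0% to 97%.

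**Follow-up images are not shown to be lacking.** A reader might cite section 10, where verification images are listed only if they exist. That list concerns images for sharing and for analysing detection failures. Sections 6.2.1 and 7.3 make the pre-operative recheck firm. The missing-value problem comes from lesion visibility, not from absent imaging.

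**Distance to the target is itself of interest.** For a localization device this is fair, and such a distance can be reported descriptively. It is a different quantity from migration.

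**Conclusion.** The point holds as a matter of wording. Read as written, section 6.2.1 decides migration from a landmark that treatment may move or erase. A motionless device can be counted as migrated if the centre shifts by more than 5 mm, and has no value if the lesion cannot be seen. With a shift of 5 mm or less, or concentric shrinkage without contraction, no false migration arises.

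The size cannot be fixed from the documents. The ranges above rest on assumed shifts, assumed device positions and recording of distance only.

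The consequence is limited to one descriptive secondary endpoint of a pilot with no test or threshold. A reader might infer that the primary endpoint is affected too, because it requires the device to stay in place. Section 4.1.1 does not apply the 5 mm rule or the lesion-centre measurement to that judgement, so this is not supported. Nor do the documents show that the endpoint was measured wrongly in practice. The change is worth making because it is cheap; confidence is moderate, given the broken sentence and the unseen forms.

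**What to change.** In sections 4.1.2 and 6.2.1, for the stability endpoint:

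- Define migration as displacement of the SCOUT from its position on the immediate post-placement image, compared in the same modality and view, against a pre-named reference other than the lesion centre. The image already exists under the plan: "Standard of care post-procedure image verification, audio verification, and skin marking will be performed".
- Keep distance to the lesion centre for the 1 cm placement endpoint and, if wanted, report it descriptively at later images.
- Report devices without a comparable image pair as not measurable, with their number and with best- and worst-case bounds on the stability rate.
- Reconcile the two statements of the 5 mm limit in section 6.2.1, so that it is clear whether initial placement is the baseline or the reference. No rule for notifying the surgeon is proposed here.

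The cost is protocol and form wording, with measurements taken on the same routine images. The downside is that landmark positions vary with patient positioning, and the documents do not show how accurate they are at 5 mm. Some patients may also lack matched views. One measurement error may therefore partly replace another; the reported count of unmeasurable devices shows the missing-view part of this, while landmark accuracy remains unverified.
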